### 8.6 SAFETY OVERSIGHT

Independent oversight is an important component to ensure human subjects' protection. Safety oversight will be under the direction of the sponsor and a medical monitor.

## 9 CLINICAL MONITORING

Clinical site monitoring is conducted to ensure that the rights and well-being of human subjects are protected, that the reported trial data are accurate, complete, and verifiable, and that the conduct of the trial is in compliance with the currently approved protocol/amendment(s), with GCP, and with applicable regulatory requirement(s).

- Monitoring for this study will be performed by the sponsor or designate.
- On-site monitoring will occur within 4 weeks of first enrolled subject and will occur at a frequency described in the Monitoring Plan.
- Variables to be monitored will be described in the Monitoring Plan.
- The Study Director or designate will be provided copies of monitoring reports within 15 business days of visit.

## 10 STATISTICAL CONSIDERATIONS

### 10.1 STATISTICAL AND ANALYTICAL PLANS

The Statistical and Analytical Plans (SAP) may be revised during the study to accommodate Clinical Trial Protocol Amendments and to make changes to adapt to unexpected issues in study execution and data that affect planned analyses. If revised, a formal Statistical and Analytical Plans (SAP) will be completed and issued prior to database lock and unblinding of the study data.

### 10.2 ANALYSIS DATASETS

Temperature and safety analyses will be carried out on all subjects.

### 10.3 DESCRIPTION OF STATISTICAL METHODS

#### 10.4.1 GENERAL APPROACH

This is an open-label, comparative feasibility study of an investigational LED device and a diode laser device for non-invasive lipolysis of the flanks.

Mean temperature reading from each device and each thermocouple will be calculated and temperature differences will be determined.

The safety analysis will be done by analyzing spontaneous reports of adverse events (AE), subjects' completed 10 cm discomfort/pain VAS and short term response reports by the principal investigator from his/her observation/examination of the treated area. Appropriate Medical Dictionary for Regulatory Activities (MedDRA) code will be used to describe all spontaneously reported or other study related adverse events.

Summaries of spontaneously reported or other study related adverse events will be presented as:

- Number (%) of subjects with any AE,
- Number (%) of subjects with any serious adverse events (SAE),
- Number (%) of subjects permanently withdrawn from treatment due to AE

Summaries of analysis of immediate and short term response reports by the principal investigator examination will be displayed on a bar or pie chart as;

- the overall frequency of subjects with each event (pain during treatment, hemorrhage, burn, erythema, edema, purpura)
- Frequency of subjects with specific severity/intensity for each event using a 5 points scale: 1=none; 2=trace; 3=moderate; 4=marked; 5=severe
- The overall percentage or proportion of subject observed with marked or severe intensity of any event will be calculated and compared to those with none, trace or moderate severity/intensity with the aid of a bar or pie chart.

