## PROTOCOL SUMMARY

TITLE	Feasibility Study of a 950 nm Wavelength LED Device for Non-invasive Lipolysis of the Flanks
SUMMARY	Open-label, feasibility study comparing the tissue temperature profile of a 950 nm LED device and a 1060 nm diode laser for non-invasive lipolysis of the flanks. The study will enroll up to 10 subjects requesting non-invasive lipolysis of the flanks. Each subjects will receive a single treatment with each device on opposite flanks. Tissue temperatures in the treated areas will be recorded and compared.
OBJECTIVES	The objective of this clinical study is to compare the tissue temperature profiles of the LED device and diode laser device and to compare safety in the treatment of lipolysis of the flanks.
ENDPOINT	Primary objective 

• Temperature profile comparison at various tissue depths.

 Safety 

• Subject's assessment of discomfort and pain as measured by a 10 cm visual analog scale (VAS).

• Subjects experiencing a treatment-related adverse event (AE).

POPULATION	The study will enroll up to 10 male and female subjects, ≥ 18 years of age who are seeking non-invasive lipolysis of the flanks.
PHASE	Feasibility
NUMBER OF SITES	one
DESCRIPTION OF DEVICE	The investigational device uses LED technology. The 1060 nm diode laser has been approved by the FDA for non-invasive lipolysis of the flanks.
STUDY DURATION	Two months
PARTICIPANT DURATION	One day plus a telephone follow-up after one week

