## 2 INTRODUCTION: BACKGROUND INFORMATION AND SCIENTIFIC RATIONALE

### 2.1 BACKGROUND INFORMATION

Non-invasive body contouring is gaining popularity in the United States and the field is advancing at a fast pace with the vast majority of cases using non-invasive methods. Various technologies exist today including cryolipolysis, radiofrequency, ultrasound, injection lipolysis and laser. When advancing to a non-invasive approach to lipolysis, an external device is required. In 2015, the FDA approved a 1060 nm diode laser for fat reduction (Cynosure SculpSure). The laser leads to injury of the adipocytes through direct heating of the tissue. Energy creates movement within the molecules of the exposed tissue, which then generates heat. A controlled temperature of 42-47 °C must be maintained at the site of adipocytes. At this temperature, the cell membranes of the adipocytes lose their structural integrity leading to cell death. Upon cell injury and death, the body naturally eliminates the contents of the adipocytes. The laser targets unwanted adipocytes while leaving the overlying skin and adnexal structures unharmed. In addition, melanin is minimally targeted so the device can be used in all skin types.

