### 2.2 RATIONALE

A new emerging technology in the area of aesthetic medicals device is LED (light-emitting diode) photo-modulation. It is currently being used to stimulate fibroblasts to produce collagen and to destroy bacteria on the skin. In this study, a 950 nm LED investigational device is being evaluated to determine if it is able to target adipocytes by maintaining a controlled temperature of 42-47 °C, similar to the reference device. In addition, the safety of the LED device will be compared to the reference device.

The use of this LED device has been determined to present non-significant risk for the intended use in this study, because the device is not:

- Intended as an implant and presents a potential for serious risk to the health, safety, or welfare of a subject;
- Is purported or represented to be for use supporting or sustaining human life and presents a potential for serious risk to the health, safety, or welfare of a subject;
- Is for a use of substantial importance in diagnosing, curing, mitigating, or treating disease, or otherwise preventing impairment of human health and presents a potential for serious risk to the health, safety, or welfare of a subject; or
- Otherwise presents a potential for serious risk to the health, safety, or welfare of a subject.

This study will be conducted in compliance with the protocol and according to Good Clinical Practice standards.

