#### 4.2.1 PRIMARY ENDPOINTS

Tissue temperature profiles compared to the reference device.

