#### **Treatment**

Based on the mild nature of treatment, anesthesia is not required. Treatment procedure should include positioning of the patient in a manner that enables access to the target treatment anatomical site. A water-based spray should be applied to the treatment area immediately prior to treatment.

Each subject will receive two consecutive treatments in the following order: the left flank of the abdomen will be treated with the diode laser device and the right flank of the abdomen will be treated with the LED device. The exact placement on the flank will be left to the principal investigator's judgement based on his assessment of individual subject requirements for treatment. Subjects will be treated on the same bilateral location with each device to ensure consistency of measurements. Both laser and LED applicators will be set to same output power level. Two levels will be used 41W (1.17W/cm^2) and 29W (0.83W/cm^2). The first level of 41W corresponds to initial heating for 4 minutes and the second level corresponds to duty cycle of 25 sec on and 10 sec off time. Total treatment time with each device will be 24 minutes (first 4 min at full power and next 16 min at duty cycle 25/10). Both device applicators have same output window dimensions and area 7x5 cm (35 cm^2). Both applicators are cooled by water chiller and therefore provided the same surface cooling temperature on skin.

Immediately (within 2 minutes) after treatment, 3 sterile thermocouple needles of different lengths (7-15 mm), will be inserted into the center of each applicator footprint. Temperature readings from each thermocouple needle will be recorded.

During treatment, subject reaction must be monitored and if the subjects verbally report an intolerable level of pain, treatment shall be ceased immediately.

The normal response to these treatments is transient erythema and edema. If any side effects occur other than a normal transient response, as indicated in the protocol, they will be recorded.

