#### 10.4 SAMPLE SIZE

Since this is a feasibility study, no formal sample size calculation is required. The study will recruit up to 10 subjects.

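### The primary temperature comparison gives means and differences with no SD, interval or stated use of the pairing, so it cannot show which device differences the data exclude

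*Combined protocol and SAP*

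**What the plan says.** The primary endpoint in Section 4.2.1 is comparative: "Tissue temperature profiles compared to the reference device". Section 2.2 gives the scientific question as whether the LED device can target fat cells by "maintaining a controlled temperature of 42-47 °C, similar to the reference device". The Protocol Summary adds a second comparative aim, "to compare safety in the treatment of lipolysis of the flanks".

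The design is paired within subject. Under Treatment in Section 7.3.2 the sides are fixed: "the left flank of the abdomen will be treated with the diode laser device and the right flank of the abdomen will be treated with" (LED on the right). Three thermocouple needles of different lengths (7-15 mm) are then read on each side.

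The analysis in Section 10.3 (subsection General Approach, numbered 10.4.1) is one sentence for temperature: "Mean temperature reading from each device and each thermocouple will be calculated and temperature differences will be determined". For safety it lists counts and percentages of subjects with AEs, and charts of the investigator's graded responses. It names the VAS but gives no summary statistic for it.

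Section 10.4 says "Since this is a feasibility study, no formal sample size calculation is required" and "The study will recruit up to 10 subjects". Section 10.1 allows the analysis plan to be revised but commits to no measure of uncertainty. ANCOVA and LSMEANS are in the abbreviation list but in no method.

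**The concern.** A comparison needs an estimate and a statement of how well it is known. The plan commits only to the estimate. A mean difference of, say, 0.5 °C at one depth could come from ten subjects whose differences all lie close to that value, or from a few subjects whose differences scatter over several degrees. The planned output would look the same in both cases.

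The pairing matters for the same reason. Putting both devices on one subject removes between-subject variation from the comparison, but the gain appears only if the spread of the within-subject differences is reported. Separate device means do not show it, and separate device SDs would not either. That paired SD is also a quantity a feasibility study is well placed to supply for sizing a later trial.

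Comparative safety has less support still. Every subject receives both devices, yet AEs are to be counted per subject. Such a count cannot be divided between devices.

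**Working it through.** **Figure to reproduce.** There is none. Section 10.4 states the maximum of 10 subjects with no SD, margin, error rate or power, and says that no calculation was made. The check is therefore of the precision the design can give.

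**Inputs.**
- n: at most 10 (Section 10.4). No minimum is stated, so n = 5 is shown as a permitted lower case, not a planned one.
- Design: one LED and one laser reading per subject at each depth, hence n paired differences per depth.
- SD of the paired difference: not in the documents. **Assumed** to be 1 to 3 °C.

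**Formula.** The half-width of the 95% CI for a mean paired difference is t(0.975, n − 1) × SD / √n.

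- n = 10: t(0.975, 9)/√10 = 0.715, so the half-width is 0.715 × SD.
- n = 5: t(0.975, 4)/√5 = 1.242, so the half-width is 1.242 × SD.

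| Assumed SD of difference | n = 10 | n = 5 |
|---|---|---|
| 1 °C | ±0.72 °C | ±1.24 °C |
| 2 °C | ±1.43 °C | ±2.48 °C |
| 3 °C | ±2.15 °C | ±3.72 °C |

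These are intervals for a single depth, with no adjustment for the three depths.

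**What one observed result would mean.** Take an observed mean difference of 1 °C at n = 10. The upper 95% limit is 1 + 1.43 = 2.43 °C if the SD is 2 °C, and 1 + 2.15 = 3.15 °C if it is 3 °C. The planned output would be 1 °C in both cases.

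**Pairing.** With complete data, the difference between the two device means equals the mean of the within-subject differences, so the point estimate is unaffected. The standard error is affected, because it depends on the correlation between a subject's two flanks. If a subject has a reading on one side only, the two estimates can also differ. Section 10.2 analyses all subjects and gives no rule for a missing reading.

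**Safety.** With no events in 10 subjects, the exact two-sided 95% upper limit is 1 − 0.025^(1/10) = 0.308, or 30.8%. If no event occurs on either flank, that limit applies to each device's own proportion. Applied to the planned per-subject count, it says nothing about one device against the other.

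**The case against.** The strongest reply is that this is a declared feasibility study. Descriptive summaries are legitimate, no sample size calculation is needed, and individual readings are recorded, so SDs and intervals could be computed afterwards without loss of data. All of that stands. The point does not ask for more subjects or for a hypothesis test. It asks that the plan commit to the summary that makes the comparison readable.

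It can also be said that the stated differences are naturally read as within-subject ones, since both devices are placed at matching sites. That is a fair reading, but the text does not say it.

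Three stronger readings are tempting, and the documents do not support them.

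- *That the data cannot exclude differences as large as much of the 42-47 °C window.* This depends on an SD the documents do not give. At n = 10, an SD of 1 to 3 °C gives half-widths of 14% to 43% of the 5 °C width. Half the width (2.5 °C) is reached only at an SD of about 3.5 °C, or about 2 °C at n = 5. The window is also not a margin for a device difference. Section 2.1 makes it an absolute target: "A controlled temperature of 42-47 °C must be maintained at the site of adipocytes". Two devices can agree and both miss it, or differ by much less than 5 °C with only one inside it.
- *That the protocol plans to declare similarity or comparable safety.* It states no margin or decision rule. The word similar is in the rationale, where it can be read as describing the temperature range itself. A reader of the results could draw such a conclusion, but the plan does not say that one will be drawn.
- *That a paired interval makes the comparison one of devices alone.* The laser is always on the left and is listed first, and the LED is always on the right. The interval carries any side or order effect with it.

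**Conclusion.** The point holds as a gap in the analysis plan. The primary comparison as written has no measure of uncertainty and does not state that the pairing will be used, so it cannot show what device differences the data exclude. How much this matters numerically is unknown, because it rests on an assumed SD and on the number of subjects reached. Over an SD of 1 to 3 °C the half-width runs from ±0.7 °C (n = 10, SD 1 °C) to ±3.7 °C (n = 5, SD 3 °C). The upper end needs both the largest assumed SD and half the maximum enrolment. The case for the change is that readers would not know where in this range the study fell. The safety comparison has the further defect that its AE summaries are not by device. The plan should be changed, but the gap does not invalidate a feasibility study.

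**What to change.** In Section 10.3:

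- At each thermocouple depth, report the LED minus laser difference within subject: number of pairs, mean, SD and paired-t 95% CI. List or plot the individual readings for each device against 42-47 °C, so that the absolute target is addressed separately from the difference.
- Summarise local AEs, VAS and the investigator's graded responses by treated flank, and so by device. Give within-subject differences for VAS and exact 95% CIs for per-device AE proportions. The VAS is already taken after one treatment and before the next. The AE items listed in Sections 8.3 and 8.4.1 do not name the side, so the AE form should record it for local events.

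In Sections 10.3 and 10.4, state that the results are estimates, that no equivalence or comparable-safety conclusion will be drawn, and that the interval does not separate device from the fixed side and treatment order.

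The cost is some plan wording, a few table columns, one field on the AE form and a slightly more modest claim. No subjects or procedures are added.

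### Section 10.3 gives no device split for AEs or graded skin responses, and its one stated safety comparison is between severity groups, so as written these rows do not compare LED with laser

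*Combined protocol and SAP*

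**What the plan says.** The Protocol Summary gives as an objective "to compare safety in the treatment of lipolysis of the flanks", alongside the temperature comparison. Section 2.2 is more direct: "the safety of the LED device will be compared to the reference device".

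The design is within-subject. Section 7.3.2 (Treatment) states: "Each subject will receive two consecutive treatments in the following order", with the diode laser on the left flank and then the LED on the right.

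Section 10.3 (General Approach) treats the two kinds of outcome differently. For temperature the device is explicit: "Mean temperature reading from each device and each thermocouple will be calculated and temperature differences will be determined". For safety there are six listed summaries.

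- Three concern AEs. They include "Number (%) of subjects with any AE" and "Number (%) of subjects permanently withdrawn from treatment due to AE"; the third is the same count for serious AEs (SAEs).
- Three concern the investigator's immediate and short-term findings: how many subjects had each event, "Frequency of subjects with specific severity/intensity for each event using a 5 points scale", and the comparison "proportion of subject observed with marked or severe intensity of any event will be calculated and compared to those with none, trace or moderate" intensity.

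The VAS is named as part of the safety analysis, but no summary statistic, unit or contrast is given for it.

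**The concern.** In a parallel-group trial, counting subjects would automatically give counts by device. Here each subject belongs to both devices, so a count of subjects with an event says nothing about device unless a split is specified. Section 10.3 specifies one for temperature and not for AEs or graded responses. The one place where it names a safety comparison, it names a different one.

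Two consequences follow if the rows are produced literally, with each subject counted once.

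- The same table results whether the reactions arose under the LED, under the laser or under both. Burns, blistering and scarring are among the expected reactions in 8.2.3, so which device produced them is the safety question.
- The severity row has no defined value for a subject whose two flanks differ, for example erythema graded 4 on one side and 2 on the other. The plan does not say whether the worse flank, each flank or some average is used.

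The discontinuation row has a further problem. The laser is listed first, and treatment stops if pain becomes intolerable. The row would not show which device led to the stop, nor whether the LED was ever applied.

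**Working it through.** The plan has no figure to reproduce: it states no event rates, alpha, power or safety margin. The check is a reading of the rows, then an enumeration of what those rows can and cannot show.

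**Inputs.** Up to 10 subjects (10.4 Sample Size); the enumeration uses n = 10. Both devices in every subject (7.3.2). Rows as listed in 10.3. The event counts and rates below are illustrative assumptions.

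**Step 1. Is a device named?**

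| Item in 10.3 | Unit stated | Device or flank stated |
|---|---|---|
| Temperature | device and thermocouple | yes |
| Any AE; any SAE; withdrawn for AE | subject | no |
| Each graded event; each grade; marked/severe | subject | no |
| VAS | none | no |

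No other section supplies a by-device safety table.

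**Step 2. What the stated comparison measures.** Let k be the number of subjects with a marked or severe event on either flank. The comparison is k/10 against (10 - k)/10. The second is 1 minus the first, so the comparison adds nothing to k and contains no device term.

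**Step 3. What a subject-level count leaves open.** Split k = a + b + c, where a is LED only, b is laser only and c is both. The device counts are LED = a + c and laser = b + c, so LED minus laser = a - b, which runs from -k to +k. The number of distinct pairs of device counts is (k + 1)(k + 2)/2.

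- k = 0: 1 pair, difference fixed at 0.
- k = 3: 4 × 5 / 2 = 10 pairs, difference -30 to +30 points.
- k = 6: 7 × 8 / 2 = 28 pairs, difference -60 to +60 points.

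At k = 3 the LED could be 0/10 (exact 95% CI 0 to 31%) or 3/10 (7 to 65%). At k = 6 the data could be 6 v 0 in either direction (exact McNemar p = 2 × 0.5^6 = 0.031) or 6 v 6, with no difference at all.

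**Step 4. A subject-level rate is not either device's rate.** Suppose each device's true rate is 20%. The share of subjects with an event on either flank is then 20% if the events always coincide, 1 - 0.8^2 = 36% if the flanks are independent, and 40% if they never coincide.

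**Step 5. What a by-device table would deliver.** With the four-way split reported, a - b is known exactly. At n = 10 it stays descriptive: 5 discordant subjects all in one direction give p = 2 × 0.5^5 = 0.063, and 6 give 0.031. At a conventional 0.05 level (my assumption) at least 6 one-way discordant subjects would be needed.

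**The case against.** The strongest reply is that silence is not pooling. Section 10.3 opens by calling the study comparative, and a row counting subjects with an AE is a normal label in a table that has one column per device. The text nowhere says that flanks are combined. This stands in part: pooling is the literal reading of the rows, not a stated instruction, so the results in Steps 2 to 4 hold only if each subject is counted once across both flanks. It does not rescue the explicit severity comparison, which even within a device column would compare severity groups and not devices.

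A reader might infer that the plan rules out any safety comparison between devices. The documents do not support that. The VAS is taken soon after a treatment and before any further one (7.3.2, Assessment), which points to a reading per device. It is under-specified, but it is not shown to be pooled.

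A reader might equally infer that side-specific data are certain to be available, so that nothing is lost. That is not supported either. The AE items in 8.3 and 8.4.1 do not include flank or device, and the Assessment text speaks of the treated area without saying that each flank is graded separately. Capture by side is likely but not guaranteed.

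The feasibility label is a fair defence against asking for power or a formal test, and none is asked for. It does not excuse leaving out by-device counts for a stated objective. It is also fair that AEs are recorded individually with an assessment of relatedness, so a careful sponsor could re-cut the data. That limits the harm, and it is why the point is minor.

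**Conclusion.** The point holds for the AE and investigator-graded response summaries as written. They name no device or flank, and the one stated safety comparison is between severity groups. Followed literally, they cannot deliver the stated comparison of LED with laser safety for any count above zero: a row of 3/10 leaves the difference anywhere from -30 to +30 points. The VAS is a lesser gap, since it could be compared by device but has no stated summary.

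Severity is minor. There are at most 10 subjects, no test or decision rule rests on these rows, and the within-subject design can support the comparison if the forms record side. The sizes quoted assume 10 subjects, each counted once across both flanks, and illustrative event counts. They show how much the rows leave open; they do not predict harm.

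**What to change.** In 10.3:

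- Report local AEs, SAEs, investigator grades and treatment discontinuations by device. Use the flanks actually treated with that device as the denominator, not a fixed 10: enrolment may be lower, and a subject who stops during the laser session may never receive the LED.
- List systemic AEs that cannot be assigned to one device on a separate line.
- Replace the severity-group comparison with a within-subject table of marked or severe events (LED only, laser only, both, neither) among subjects treated with both devices.
- Summarise the VAS by device, with the paired difference.
- State that all of this is descriptive.

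Make sure that the AE form and the response-grading form each record flank or device.

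The cost is a rewrite of the safety rows and one form field, with no extra subjects, visits or measurements. Section 10.1 already allows the analysis plan to be revised before database lock. The form field should be in place before the first treatment.

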## 3 OBJECTIVES AND PURPOSE

The study is being conducted to evaluate the feasibility and safety of a LED device for non-invasive treatment of the flanks.

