### Safety

Subject's assessment of discomfort and pain as measured by a 10 cm visual analog scale (VAS).

Subjects experiencing a treatment-related adverse event (AE).

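### Safety is to be compared between the LED and the laser, but the adverse-event and reaction-score displays count subjects who all received both devices, with no split by device

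*Combined protocol and SAP*

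**What the plan says.** The aim is stated comparatively in two places. The Protocol Summary gives the objective as comparing temperature profiles and "to compare safety in the treatment of lipolysis of the flanks". Section 2.2 (Rationale) says that "the safety of the LED device will be compared to the reference device". Section 4.1 also calls the study comparative.

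Under Treatment in Section 7.3.2, each subject has the laser on the left flank and then the LED on the right. Up to 10 subjects are enrolled (Section 10.4, Sample Size).

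The analysis text is in Section 10.3, under General Approach (numbered 10.4.1):

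- **Temperature:** "Mean temperature reading from each device and each thermocouple will be calculated", and differences are then taken. This is split by device.
- **Adverse events:** three summaries, beginning with "Number (%) of subjects with any AE" and going on to subjects with any SAE and subjects withdrawn because of an AE.
- **Investigator's reaction scores:** three displays, namely "the overall frequency of subjects with each event", the frequency of subjects at each severity, and the overall proportion of "subject observed with marked or severe intensity of any event will be calculated and compared to those with none, trace or moderate severity/intensity".
- **VAS:** named as part of the safety analysis, with no statistic and no device contrast.

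The objectives are not uniform. Section 3 speaks of a study to "evaluate the feasibility and safety of a LED device for non-invasive treatment of the flanks", with no comparator. The safety items in Sections 3 and 4.2.2 are worded per subject.

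**The concern.** In a split-body design, a count of subjects merges the two arms: a subject with a burn on the laser side and one with a burn on the LED side add the same unit to the same total. None of the AE or reaction-score displays names device, flank or applicator, and Section 10.2 defines only one analysis set, all subjects. The single comparison described for safety is between severity categories, not between devices.

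The stated safety comparison therefore cannot be read from the planned output. The displays say least about the devices where reactions are common, and Section 7.3.2 describes transient erythema and edema as the normal response to both treatments.

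**Working it through.** The plan has no figure to reproduce: Section 10.4 states that no sample-size calculation was made. The check is a reading of the text followed by an illustrative enumeration.

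**Text.** Section 10.3 specifies the device for temperature and does not do so for any safety item. No other section adds a by-device safety summary. Two of the three reaction-score displays are expressly labelled overall.

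**What a subject count can show.** Inputs: n = 10 subjects (the stated maximum), each with one LED flank and one laser flank. Assumption, because the plan gives no rule for combining flanks: a subject is counted if either flank reacts. Let k subjects be counted, of whom a reacted on the LED side only, b on the laser side only and c on both, so that a + b + c = k.

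- LED count = a + c; laser count = b + c.
- Number of distinct (LED, laser) pairs that give the same k: (k + 1)(k + 2)/2.
- Range of the LED-minus-laser difference: -k/n to +k/n.

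| k of 10 | Pairs that fit | LED minus laser, percentage points |
|---|---|---|
| 0 | 1 × 2/2 = 1 | 0 |
| 1 | 2 × 3/2 = 3 | -10 to +10 |
| 3 | 4 × 5/2 = 10 | -30 to +30 |
| 4 | 5 × 6/2 = 15 | -40 to +40 |
| 5 | 6 × 7/2 = 21 | -50 to +50 |
| 10 | 11 × 12/2 = 66 | -100 to +100 |

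With k = 3, the plan prints 3/10 against 7/10. That print is the same for LED 3 and laser 0, LED 0 and laser 3, LED 3 and laser 3, and seven other pairs. If only 6 subjects enrol, k = 2 fits 3 × 4/2 = 6 pairs, from -33 to +33 points. Only k = 0 fixes the difference, at zero.

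**What a by-device display could show with 10 pairs.**

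- Exact (Clopper-Pearson) 95% intervals: 3/10 gives 6.7% to 65.2%; 0/10 gives 0% to 30.8%.
- Exact McNemar, all m discordant pairs in one direction, p = 2 × 0.5^m: m = 5 gives 0.0625; m = 6 gives 0.031.
- VAS mean within-subject difference, 95% half-width = 2.262/√10 × SD = 0.715 × SD. For an assumed SD of 1.0 to 2.5 cm this is 0.7 to 1.8 cm.

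**Whether the data would allow the split.** The documents do not settle this.

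- In favour: VAS is recorded within 5 minutes of a treatment and ahead of the next one (Section 7.3.2); the subject identifier is entered for each treatment (Section 7.3.2); and because sides are fixed, any recorded location identifies the device.
- Against: the investigator's score refers only to the treated area; the AE items in Sections 8.3 and 8.4.1 do not include flank or device; and relatedness in Section 8.2.2 is to a study agent that is not tied to either device.
- The CRF is not in the documents.

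**The case against.** Four points can be made for the plan.

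1. **Some of the summaries belong at subject level.** SAEs and withdrawals are properly counted once per subject, as are non-local AEs. This is right and limits the remedy: the defect bears on local AEs, reaction scores and VAS.
2. **The counting rule is assumed.** The display of severity by event is not labelled overall, and the plan does not say how two flanks become one subject value. For that display, unspecified is the fairer word. But a subject count without a device label still cannot show which device caused the reaction, whatever the combining rule.
3. **The data are probably recoverable.** The treated area is written in the singular, which fits scoring each area separately. Section 7.8 requires the chart and treatment parameters to be forwarded for burns and minor complications. Section 10.1 allows the analysis plan to be revised before database lock. These make correction cheap. They do not put a device split into the present text, and flank-level recording is not assured.
4. **The stakes are modest.** Safety is secondary, at most 10 subjects enrol, and a corrected comparison would be imprecise and confounded with side and order. That is so, and it rules out inference. It does not excuse leaving out the description of each device, which is the main thing a study of this size can provide.

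**Conclusion.** The concern holds, and the plan should be changed. A stated objective, the comparison of LED safety with laser safety, cannot be answered from the AE and reaction-score displays as specified, and no statistic is given for the VAS. In the illustration, a printed 3/10 is compatible with any device difference from -30 to +30 percentage points and 10/10 with any from -100 to +100. These ranges rest on invented counts and on counting a subject if either flank reacts; they show what the display hides and are not an expected effect.

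The primary temperature endpoint, the sample size and the error rates are not affected. If flank or device is recorded, the split can be recovered from at most 10 subjects' records, but nothing in the plan asks for it.

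**What to change.** In Section 10.3:

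- Show local AEs and each 5-point reaction score by device (treated flank), at each time point scored, with the flanks treated by that device as denominator.
- Replace the comparison of marked/severe with its complement by the marked/severe proportion for LED beside that for laser, adding a paired within-subject table if wanted.
- Report VAS by device with the mean within-subject difference.
- List non-local events, SAEs and withdrawals once per subject.
- State that the comparison is descriptive and that device is confounded with side and order (laser left first, LED right second). A by-device display does not remove that confounding.

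Align the safety wording in Sections 3 and 4.2.2 with the comparison in the Protocol Summary and Section 2.2. Before the first treatment, confirm that the reaction-score and AE forms record flank or device, and add the field if they do not. The planned follow-up is a telephone contact, so a location missed on the day may be hard to recover.

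The cost is wording, slightly longer tables and possibly one CRF field, with no new visits, procedures or subjects. The by-device figures will remain imprecise, as the intervals above show, and should be read as description only.
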